5.4.4.3 Neuroimaging History

Neuroimaging history data will be listed only.

5.4.5 Medical and Surgical History and Current Medical Conditions

All conditions and diagnoses on the 'non-epilepsy medical history' CRF page will be coded using Version 19.1 of the Medical Dictionary for Regulatory Activities (MedDRA v19.1).

The number of patients with relevant or significant non-epilepsy medical or surgical history and medical history by system organ class, and preferred term, will be summarized by absolute counts (n) and percentages (%). Percentages will be calculated based on the number of patients in the specific treatment arm. Two tables will be produced, one including any events classified as resolved at screening, and the other including all current conditions.

5.5 Efficacy Analysis

5.5.1 General Approach

Blinded Phase:

The primary analyses will use the ITT analysis set. Further analyses using the PP analysis set will also be performed for the primary endpoint and secondary endpoints where specified in the sections below.

The primary null hypothesis is:

- Following 16 weeks of treatment there is no difference in effect between the 25 mg/kg/day GWP42003-P treatment arm and the placebo treatment arm in terms of the change in number of TSC-associated seizures during the treatment period compared to baseline.

The null hypothesis will be rejected if there is statistical evidence of a difference between the treatment arms at the α -level of 0.05 for the primary endpoint.

Statistical hypothesis testing will be performed on the primary endpoint and other endpoints as appropriate. Each endpoint, including the primary will have 2 comparisons against placebo (25 mg/kg/day GWP42003-P vs. placebo and 50 mg/kg/day GWP42003-P vs. placebo). Also, 3 key secondary endpoints have been defined.

The primary and key secondary endpoints will be tested with their Type I error controlled by use of a hierarchical gate-keeping procedure, in the sequence given in Table 3. One must reject the null hypothesis of an endpoint at the level of 0.05 (2-sided) to test the hypothesis of the subsequent endpoint in the sequence at the level of 0.05 (2-sided). If a null hypothesis is not rejected then testing will stop and all subsequent analyses will be declared not statistically significant.

Table 3 Hierarchy for Analysis

Test	Endpoint	Treatment Comparison
1	Primary endpoint	25 mg/kg/day GWP42003-P vs. Placebo
2	1 st key secondary endpoint	25 mg/kg/day GWP42003-P vs. Placebo
3	Primary endpoint	50 mg/kg/day GWP42003-P vs. Placebo
4	1 st key secondary endpoint	50 mg/kg/day GWP42003-P vs. Placebo
5	2 nd key secondary endpoint	25 mg/kg/day GWP42003-P vs. Placebo

6	3 rd key secondary endpoint	25 mg/kg/day GWP42003-P vs. Placebo
7	2 nd key secondary endpoint	50 mg/kg/day GWP42003-P vs. Placebo
8	3 rd key secondary endpoint	50 mg/kg/day GWP42003-P vs. Placebo

All statistical tests will be 2-sided and use the 5% significance level.

The assumptions of normality and homogeneity of variance, for endpoints analyzed using parametric tests, will be checked where appropriate via examination of residual plots as well as computation of summary statistics for normality using the Shapiro-Wilk statistical test. If assumptions are violated then alternative non-parametric techniques will be used. In this instance the original parametric tests will be presented as a sensitivity analysis.

Open-label Extension:

All endpoints will be summarized on the OLE safety analysis set, unless specified otherwise.

Endpoints will be summarized by treatment received during the double-blind phase (GWP42003-P or Placebo, i.e. not split by dose) and overall.

For seizure endpoints, the OLE treatment phase will be split into 12 week periods, for example:

- OLE Week 1 (OLE Day 1) to OLE Week 12 (Day 84)
- OLE Week 13 (OLE Day 85) to OLE Week 24 (OLE Day 168)
- OLE Week 25 (OLE Day 169) to OLE Week 36 (OLE Day 252)
- OLE Week 37 (OLE Day 253) to OLE Week 48 (OLE Day 336)
- OLE Week 49 (OLE Day 337) to OLE Week 60 (OLE Day 420)
- Etc.

In addition, seizure data will be presented for the full OLE treatment phase as well as the last 12 weeks of the OLE treatment phase (see Section 5.1.3.3).

5.5.2 Primary Efficacy Endpoint

Blinded Phase:

The primary endpoint is the change in number of TSC-associated seizures (see Section 5.1.3.7) during the treatment period (see Section 5.1.3.4) compared to baseline period (see Section 5.1.3.1) in patients taking GWP42003-P compared with placebo.

The primary endpoint will be analyzed using a negative binomial regression model with the total number of TSC-associated seizures during the baseline period and treatment period as the response variables.

A mixed effect model with repeated measures will be performed modelling the observed total number of TSC-associated seizures in the baseline period and treatment period implemented within the framework of general linear models using the negative binomial response distribution. The model will include stratified age group (1–6 years, 7–11 years, 12–17 years and 18–65 years), time, treatment arm and treatment arm by time interaction as fixed effects and patient as a random effect. The log transformed number of days in which seizure data were reported will be included as an offset. The time variable corresponds to an indicator for the baseline period and treatment period.

The GLIMMIX procedure in SAS will be utilized to perform the analysis with the option maxopt=300 applied. If the model fails to converge, then the statement 'nloptions tech=nrrridg;' will be added. If convergence is still not achieved, then 'method=laplace' will be utilized. However, if convergence is still not possible, then the model will be changed to utilize the log normal response distribution (log rate model). If the log rate model is required and there are patients with no seizures during the baseline or treatment period then all patients will have their baseline and treatment period seizure count adjusted by adding a value of 1.

The estimated least squares mean seizure rate for each period and the estimated ratio of least squares means for treatment period to baseline period and 95% confidence intervals (CIs) will be presented for each treatment arm. In addition, the estimated ratio of each GWP42003-P arm to placebo and 95% CIs will be presented along with the p-value testing the null hypothesis that this ratio is 1.

For each ratio and upper and lower bound of the 95% CI, the percentage reduction will also be presented, calculated as:

$$[1 - (X \div Y)] \times 100\%$$

Where X corresponds to the treatment period estimate, or GWP42003-P ratio, and Y corresponds to the baseline period estimate, or placebo arm ratio.

Primary efficacy analysis will be performed using the ITT analysis set.

TSC-associated seizure frequency (28-day average) and percentage change in seizure frequency will also be presented using summary statistics. Percentage change from baseline in TSC-associated seizure frequency will be calculated as:

$$((\text{Frequency during the treatment period} - \text{Frequency during baseline}) \div \text{Frequency during baseline}) \times 100$$

The frequency during each period will be based on 28 day averages and calculated as:

$$(\text{Number of seizures in the period} \div \text{Number of reported days in IVRS in the period}) \times 28$$

For the TSC-associated seizure endpoints only, if patients are randomized with no TSC-associated seizures during the baseline period then the percentage change from baseline will be calculated as:

$$(\text{Frequency during the treatment period} + 1) \times 100$$

Open-label Extension:

The primary endpoint for the OLE is the safety of GWP42003-P, evaluated by assessing the incidence, type and severity of AEs. Data will be presented as per Section 5.6.2.

However, percentage change from baseline in TSC-associated seizure frequency is considered a key secondary endpoint for the OLE.

In the OLE, seizures are recorded on a weekly basis rather than daily. Caregivers/patients are expected to call the IVRS system to record the number of seizure subtypes experienced every 7 days during the OLE. TSC-associated seizure frequency per 28 days will be calculated for each of the periods described in Section 5.5.1. All calls that take place during the period in question will contribute to the calculation of the average number of seizures per day in that period only.

The average number of seizures per day in the period will be calculated as the average of:

$$\text{Number of seizures reported} \div \text{Number of days since last IVRS call}$$

The number of days since the last call will be calculated as follows, and is dependent on whether the call took place <7 , 7 or >7 days after the previous call (or after the date of OLE Day 1 in the case of the first call in the first period):

- If the call takes place exactly 7 days after the previous call, then the number of days since the last call will be 7.
- If the call takes place <7 days after the previous call, then the number of days since the last call will be calculated as:
$$(\text{Date of current call} - \text{date of previous call}) + 1$$
- If the call takes place >7 days after the previous call, then the number of days since the last call will be 7.

Summary statistics will be presented for raw seizure frequencies and percentage change from baseline (from the blinded phase).

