Epileptic seizures are the most common clinical manifestation of TSC, affecting more than 70% of patients. Seizure onset occurs within the first year of life in approximately two-thirds of TSC patients and occurs within the first 3 years of life in 80% of TSC patients. The onset of epilepsy in TSC commonly manifests as focal motor seizures, which in approximately one-third of TSC patients coexist with infantile spasms. Interictal electroencephalogram (EEG) recordings at onset typically show hypsarrhythmia, characterized by focal or multifocal spike discharges and irregular slow-wave activity. Virtually all TSC patients with infantile spasms and approximately half of all epileptic TSC patients without them develop multiple seizure types, including complex focal seizures (with or without secondary generalization), generalized tonic-clonic seizures, atonic seizures, and atypical absences. Although infantile spasms resolve with time, the frequency and severity of other seizures tend to increase throughout early childhood and nearly two-thirds of TSC patients develop medically intractable epilepsy, including Lennox-Gastaut syndrome. Cognitive impairment (intelligence/developmental quotient < 70) is observed in around 60% of all TSC patients with a history of seizures and in approximately three-quarters of all TSC patients with a history of refractory epilepsy. Early management of seizures is therefore important in preventing subsequent epileptic encephalopathy and in reducing the associated cognitive and neuropsychiatric consequences.

In both the European Union and the United States, the drug of first choice for the treatment of infantile spasms secondary to TSC is vigabatrin (VGB), which was approved by the U.S. Food and Drug Administration (FDA) in 2009 (as Sabril®) to treat infantile spasms in children aged 1 month to 2 years. VGB is a structural analog of  $\gamma$ -aminobutyric acid (GABA; the major inhibitory neurotransmitter in the central nervous system) that irreversibly inhibits GABA-transaminase and thereby increases brain levels of GABA. The initial prospective clinical study compared VGB (100–150 mg/kg/day) with adrenocorticotropic hormone (ACTH; 10 IU/day) in 42 patients with infantile spasms, only 4 of whom were diagnosed with TSC (3

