## 7.2 Randomization

The allocation of IMP to treatment number will be done according to a randomization schedule produced by an independent statistician. The randomization schedule will be held centrally and not divulged to any other person involved in the study until the database has been locked and unblinding authorized by the relevant GW personnel. For access to blinded treatment assignment, see Section 8.5.

The randomization will be stratified by age group (1–6 years, 7–11 years, 12–17 years and 18–65 years).

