Summaries and analyses of total seizures (see Section 5.1.3.9) will be performed as per the primary endpoint (Section 5.5.2).

The analysis will be performed on the ITT analysis set and repeated on the PP analysis set.

Sensitivity analyses will be performed on the ITT analysis set, repeating the above analysis, using data for only the maintenance period, titration period, and during each 4 weeks of the maintenance period (Week 1 to 4, Week 5 to 8 and Week 9 to 12 of the 12 week maintenance period).

Analyses on the maintenance period, titration period and by each 4 weeks of the maintenance period will include only patients who have at least 7 days of seizure data within each period.

Open-label Extension:

Summaries will be performed for the OLE periods as described in the OLE portion of the primary endpoint section (Section 5.5.2).

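### Age group enters the primary model only as a main effect, so the stratification factor does not reach the standard error of the tested arm-by-time contrast

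*SAP*

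**What the plan says.** Protocol 7.2: "The randomization will be stratified by age group", in four groups (1–6, 7–11, 12–17 and 18–65 years).

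SAP 5.5.2 carries that factor into the primary model: "The model will include stratified age group", followed by "time, treatment arm and treatment arm by time interaction as fixed effects and patient as a random effect". Protocol 13.6.2 lists the same terms. On time the SAP says: "The time variable corresponds to an indicator for the baseline period and treatment period". So each patient contributes two counts, and age group has no interaction with time.

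The tested quantity is set out in the same section: "the estimated ratio of each GWP42003-P arm to placebo and 95% CIs will be presented along with the p-value". The ratio in question is each arm's treatment-to-baseline rate ratio, so the test is of the arm-by-time term.

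The third key secondary endpoint uses the same model (SAP 5.5.3.1.3): "Summaries and analyses of total seizures (see Section 5.1.3.9) will be performed as per the primary endpoint (Section 5.5.2". In SAP Table 3 the model therefore drives tests 1, 3, 6 and 8. Testing stops at the first non-rejection.

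Elsewhere age does reach the treatment comparison. The responder test is a Cochran–Mantel–Haenszel test stratified by age (SAP 5.5.3.1.1). The rank, log and percentage-change ANCOVAs in SAP 5.5.2.1 have age as a covariate. The effect-modifier model in SAP 5.5.5 crosses each factor, age included, with time and arm.

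**The concern.** When randomization is stratified on a factor, the analysis is normally expected to condition on it, so that the standard error reflects the balance that the design secured. The primary model appears to do this because age group is listed among its terms. But a main effect of age describes how high a patient's seizure rate is, in both periods alike. The test concerns how the rate changes between periods. Differences in level are already absorbed by the patient random effect, so the age term has almost nothing left to do for the contrast.

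If age groups differ in how seizure rates change from baseline to treatment, that variation stays in the error term of the primary test although the arms were balanced on it. At stake is some efficiency in four of the eight hierarchical tests, the first of them included. The validity of the test is not at stake.

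**Working it through.** **Inputs from the documents.** 70 patients per arm with placebo pooled, reductions of 15% and 50%, common SD 60%, 90% power by Wilcoxon–Mann–Whitney (SAP 3.2). On the level: "All statistical tests will be 2-sided and use the 5% significance level" (SAP 5.5.1).

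**Step 1: the plan's own power.** Noether's formula with p = Φ(35/(60√2)) = 0.660 gives a total of (1.960 + 1.282)²/(3 × 0.160²), which is 68.4 per arm, so 69. At 70 per arm power is 90.6%. The stated 90% is reproduced, and no age adjustment enters it.

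**Step 2: why the main effect drops out.** In the log-rate fallback, write patient i's log rate in period t as level + age effect + patient effect + time and arm terms + error. The change is

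d = y(treatment) − y(baseline) = time effect + arm-by-time effect + difference of errors.

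The age and patient effects cancel. With both periods observed for everyone, the arm-by-time estimate and its SE are the same with or without age. Two simulated datasets agree: SE 0.10915 in both fits, falling to 0.0994 with age by time; and 0.1118 in both fits, falling to 0.0985.

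**Step 3: the negative binomial model.** The cancellation is only approximate here, so it was simulated with 210 patients, stratified randomization and no treatment effect. Assumptions that are not in the documents: dispersion 0.15; random-intercept SD 0.9; about 2 seizures a day; age shares 28/27/19/26%; blocks of 6; 12% with a shortened treatment period; maximum likelihood by quadrature.

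| Age predicts | Runs | Mean SE: no age / plan / plus age by time | Median SE ratio to no age: plan / plus age by time | Actual SD of estimate: plan / plus age by time | Null rejection: plan / plus age by time |
|---|---|---|---|---|---|
| level only | 480 | 0.1000 / 0.1000 / 0.0994 | 0.9997 / 0.994 | 0.0995 / 0.0995 | 0.048 / 0.054 |
| change, R² about 0.07 | 600 | 0.1039 / 0.1038 / 0.0997 | 0.998 / 0.962 | 0.0987 / 0.0985 | 0.043 / 0.053 |
| change, R² about 0.23 | 600 | 0.1133 / 0.1128 / 0.0996 | 0.996 / 0.881 | 0.1036 / 0.1023 | 0.040 / 0.062 |

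Monte Carlo error is about 0.003 on an SD and, at 600 runs, √(0.05 × 0.95/600) = 0.009 on a rejection rate. Three things follow.

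- The plan's age term moves the SE by at most about 0.4%.
- Under stratification the actual spread of the estimate is nearly the same with either model. Age by time mainly brings the reported SE down to that spread.
- The ratio of 0.994 in the first row, where no gain is possible, is a small maximum-likelihood artefact. The other ratios contain it too.

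**Step 4: size on the planning scale.** Let R² be the share of variance in change that age group explains. The SE is multiplied by √(1 − R²). With 70 × 3/π = 66.8 effective patients per arm, SE = 60√(2/66.8) = 10.38 and power = Φ(35/SE − 1.96).

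| Assumed R² | SE ratio | Power |
|---|---|---|
| 0 | 1.000 | 92.1% |
| 0.02 | 0.990 | 92.6% |
| 0.05 | 0.975 | 93.3% |
| 0.10 | 0.949 | 94.5% |
| 0.20 | 0.894 | 96.5% |

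The gain is 1.2 points at R² 0.05 and 2.4 at 0.10. These figures take the current model's reported SE as its true spread. If stratification balances age fully, the estimate already has the smaller spread, and the current model's power at R² 0.10 is Φ((35 − 1.96 × 10.38)/9.85) = 93.2%. The gain is then 94.5 − 93.2 = 1.3 points.

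**Step 5: is an R² near 0.10 plausible?** Take an assumed residual SD of 0.6 log units per period, so that a change has variance 2 × 0.36 = 0.72. Age-specific changes with SD 0.3 add 0.09, giving R² = 0.09/0.81 = 0.11 and an SE of √(0.81 × 2/70) = 0.152 against √(0.72 × 2/70) = 0.143. An SD of 0.3 over four groups means a range of roughly 0.6 to 0.8 log units. The whole planned drug effect is ln(0.50/0.85) = −0.53. So R² of 0.10 is the upper end of what one would plan for.

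**The case against.** The strongest reply is that the loss is conditional and probably small. It vanishes if age group does not predict change, and neither document gives a figure. A reader might take the protocol's background statement (3.1) that "the frequency and severity of other seizures tend to increase throughout early childhood" as proof that change depends on age in this trial. It is not: it describes natural history over years, bears mainly on the youngest stratum, and says nothing about differences between a 28-day baseline and a 16-week treatment period. This part of the objection stands.

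A reader might also infer that stratifying by age was wasted. That confuses design with analysis. Balance on age can lower the true variance of the estimate whatever model is fitted. In simulation at R² about 0.23 the SD was 0.104 with stratification and 0.109 without, in the expected direction though close to Monte Carlo error. What is missing is credit for that balance in the reported SE. Nor is the test invalid: it errs on the conservative side.

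The ANCOVA sensitivity analyses and the effect-modifier model do bring age into the comparison, as the objection says. They are not the primary test, however, and do not alter its p-value.

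Finally, the extra term is not entirely free. SAP 5.5.2 already needs a sequence of convergence fallbacks ending in a change of distribution, and the model is reused for seizure subtypes in smaller subsets. That is a reason to limit where the term is added. It is no reason to leave it out of the primary model.

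**Conclusion.** The concern holds as a modest efficiency point. The age main effect does not carry the stratification factor into the arm-by-time contrast: exactly so in the log-rate fallback with complete data, and to within about 0.4% of the SE in the negative binomial simulations. If age group predicts change, the reported SE is somewhat too large and the test mildly conservative. Type I error is not inflated, and the 90% power claim stands without age adjustment.

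The size is unknown from the documents. Over an assumed R² of 0 to 0.10 it is 0 to 5% of the SE and 0 to about 2.4 points of power, and less where stratification has already balanced age. Larger gains would need age groups to differ in change by more than the planned drug effect. The simulation results rest on the assumed dispersion, patient variance and seizure rate, and on maximum likelihood, which the SAP reaches (as a Laplace approximation) only as a fallback.

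**What to change.** Before unblinding, add age group by time to the fixed effects in SAP 5.5.2 and Protocol 13.6.2, and in the total-seizure analysis of SAP 5.5.3.1.3. Keep the current model as a named sensitivity analysis. The imputation-based repeat of the primary analysis (SAP 5.5.2.1.1) would follow automatically. For subtype analyses in small subsets, state whether the simpler model is retained. If the sponsor prefers to leave the term out, the SAP should say why.

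The cost is three degrees of freedom, one line of text in each document, no new data, and a slightly larger model in the convergence sequence. If age does not predict change, almost nothing is lost: in a log-rate check with 210 patients and stratified randomization, the SE was 0.1438 against 0.1439.

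Optionally, the arms could share one baseline mean, since baseline precedes randomized treatment. This is a separate efficiency gain. Its size depends on the correlation between baseline and treatment counts, which the documents do not give.

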5.5.2.1 Sensitivity Analyses for the Primary Efficacy Endpoint

Blinded Phase:

The following sensitivity analyses will be conducted for the primary endpoint of the blinded phase:

- Primary endpoint analysis repeated using the PP analysis set.
- Wilcoxon rank-sum test on percentage change from baseline in TSC-associated seizure frequency during the treatment period. An estimate of the median differences between each GWP42003-P arm and placebo, together with approximate 95% CIs, will be calculated using the Hodges–Lehmann approach.
- A rank analysis of covariance (ANCOVA) on percentage change from baseline in TSC-associated seizure frequency during the treatment period.

The ranks of the percentage change from baseline and the baseline TSC-associated seizure frequency will be calculated. The rank of the percentage change from baseline will then be analyzed using an ANCOVA model with the rank of the baseline TSC-associated seizure frequency and stratified age group as covariates and treatment arm as a fixed factor. The estimated least squares means, treatment differences, together with the 95% CIs and p-values will be presented.

- ANCOVA of log transformed TSC-associated seizure frequency during the treatment period.

The TSC-associated seizure frequency during the treatment period and the baseline TSC-associated seizure frequency will be log transformed prior to analysis. The log transformed TSC-associated seizure frequency during the treatment period will then be analyzed using an ANCOVA model with the log transformed baseline TSC-associated seizure frequency and stratified age group as covariates and treatment arm as a fixed factor. The back transformed estimated treatment ratios, together with the 95% CIs and p-values will be presented.

If there are any patients with no TSC-associated seizures during the baseline or treatment periods, then 1 will be added to the TSC-associated seizure frequency for all patients prior to log transformation.

- ANCOVA on percentage change from baseline in TSC-associated seizure frequency during the treatment period including baseline and stratified age group as covariates

and treatment arm as a fixed factor. The estimated least squares means, treatment differences, together with the 95% CIs and p-values will be presented.

- Primary endpoint analysis repeated using the maintenance period (see Section 5.1.3.6) rather than the treatment period.

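### The zero-baseline percentage-change formula in SAP 5.5.2 scores a patient with no seizures in either period as a doubling (+100%) instead of no change (0%)

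*SAP*

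**What the plan says.** SAP section 5.5.2 first gives the ordinary rule: "Percentage change from baseline in TSC-associated seizure frequency will be calculated as" treatment frequency minus baseline frequency, divided by baseline frequency, times 100. Positive values are increases. On the scale, it says: "The frequency during each period will be based on 28 day averages and calculated as" seizures divided by reported IVRS days, times 28. Zero seizures therefore means a frequency of zero.

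For the TSC-associated seizure endpoints only, it then adds a special case: "if patients are randomized with no TSC-associated seizures during the baseline period then the percentage change from baseline will be calculated as" (treatment-period frequency + 1) × 100. No reason is given, and there is no exception for a patient who also has no seizures on treatment. The protocol has no zero-baseline rule.

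The SAP meets zeros in two other places. In the log-transformed ANCOVA (section 5.5.2.1), if any patient has no seizures in either period, "then 1 will be added to the TSC-associated seizure frequency for all patients prior to log transformation". In the log-rate fallback for the primary model (section 5.5.2), if there are patients with no seizures in a period, "then all patients will have their baseline and treatment period seizure count adjusted by adding a value of 1". For other seizures and individual seizure types (sections 5.5.3.2.3 and 5.5.4.2), zero-baseline patients are left out of the analysis.

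**The concern.** Percentage change from a baseline of zero is undefined, so the SAP needs a convention. A convention should at least give no change to a patient who did not change, and this one does not. The expression looks like an add-1 correction in which the baseline term was never subtracted, so that it returns treatment as a percentage of baseline and not a change from baseline.

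The derived value is used in the summary statistics of section 5.5.2 and in three sensitivity analyses of section 5.5.2.1: the "Wilcoxon rank-sum test on percentage change from baseline in TSC-associated seizure frequency during the treatment period" with its Hodges–Lehmann estimate, the rank ANCOVA, and the "ANCOVA on percentage change from baseline in TSC-associated seizure frequency during the treatment period including baseline and stratified age group as covariates". It would also determine the change categories of section 5.5.3.2.1. The patients concerned stay in the ITT set, which requires only randomization and one dose (section 5.2.2).

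The error has no fixed direction. In a GWP42003-P arm it counts against the drug; in the placebo arm it counts in the drug's favour. It therefore cannot be defended as a conservative penalty.

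**Working it through.** The plan states no numerical result to reproduce here; the check evaluates its formula directly.

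**Inputs.** F is the treatment-period frequency per 28 days and B the baseline frequency (SAP 5.5.2). The treatment period is Day 1 to Day 113 (SAP 5.1.3.4). There are 70 patients per arm and a planning SD of 60%, with mean changes of −15% on placebo and −50% on GWP42003-P (SAP 3.2).

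**1. No seizures in either period.** The SAP rule gives (0 + 1) × 100 = +100%. Under the ordinary formula, +100% is the score of a patient with F = 2B: (2B − B)/B × 100 = 100. An unchanged patient, F = B, scores 0%.

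**2. General F, compared with adding 1 to both periods.** The latter gives ((F + 1) − (0 + 1))/(0 + 1) × 100 = 100F. The SAP gives 100F + 100.

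| F per 28 days | SAP rule | 1 added to both periods |
|---|---|---|
| 0 | +100% | 0% |
| 0.25 | +125% | +25% |
| 1 | +200% | +100% |
| 4 | +500% | +400% |
| 8 | +900% | +800% |

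**3. The same patient under the SAP's other zero rules.** In the log-transformed ANCOVA, baseline and treatment values both become log(0 + 1) = 0, which is a ratio of 1. In the log-rate fallback the adjusted counts are 1 and 1, again unchanged as counts. One caution applies: that rule adds to counts over periods of unequal length. If counts are divided by days, assuming 28 and 113 reported days, the rate ratio is (1/113)/(1/28) = 28/113 = 0.25, a fall. Neither rule turns this patient into an increase.

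**4. Change categories.** At 0% the patient falls in the SAP band for an increase of 0 to 25% inclusive; at +100%, in the band above 25%. One seizure in 113 fully reported days gives F = 28/113 = 0.248, so 100F = 24.8% against 124.8% under the SAP rule. Two seizures give 49.6% against 149.6%, both above 25%. With full reporting, only patients with zero or one seizure over the whole treatment period change category.

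**5. Responder test.** Neither 100F nor 100F + 100 can be negative, so a zero-baseline patient is a non-responder at ≥50% under both.

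**6. Size.** One patient with no seizures in either period shifts the mean of an arm of 70 by (100 − 0)/70 = 1.43 points. The standard error of an arm mean is 60/√70 = 7.17, so the shift is 1.43/7.17 = 0.2 standard errors. For ranks, assume normal distributions with the planning values. On placebo, 0% lies at about the 60th percentile and +100% at the 97th; on GWP42003-P they lie at about the 80th and 99th.

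**The case against.** Most of the opposing case concerns reach, and most of it stands.

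Criterion 6.1.11 requires at least eight qualifying seizures in the first 28 baseline days, and the investigator must check this from IVRS data before randomization (Protocol 9.1.1.3). A zero-baseline patient is a gross eligibility breach, and one who then has zero or one seizure over 16 weeks is rarer still. A reader might infer from the rule that such patients were randomized; the documents do not say so.

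A reader might also infer that the rule is 100 points too high for every patient it touches. That holds only against the add-1-to-both benchmark. For F > 0 no value is correct in itself. The benchmark is not quite the SAP's own convention either, because the two add-1 rules apply to all patients once triggered. Only the patient with no seizures in either period has a natural value, and it is 0%.

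Nor is it right that the patient leaves a no-change category. The protocol has such a band, but SAP 5.8 replaces it; the move is between two bands of increase.

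Finally, a reader might think that a confirmatory result is at risk. It is not. The primary endpoint and total seizures are analysed as counts, CGIC/SGIC does not use the formula, and the ≥50% responder outcome is the same under either formula. In the cumulative plots the patient is a non-reducer at every positive threshold either way.

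What the objection does not answer is the value itself: the SAP chose to provide for this case, and its formula records an unchanged patient as having doubled.

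**Conclusion.** The formula gives a wrong value for a patient with no TSC-associated seizures in both periods: +100% instead of 0%. It is also inconsistent with the SAP's own add-1 rules, which leave that patient unchanged (the log-rate fallback in terms of counts). For zero-baseline patients with seizures on treatment it is a convention lying 100 points above the add-1-to-both value, and not an error in itself.

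The consequence is small: about 1.4 points on an arm mean per patient with no seizures in either period, assuming 70 per arm, plus a shift in rank and one category. It arises only if someone was randomized in breach of criterion 6.1.11, and the number of such patients is not given. It is confined to the percentage-change summaries, the three sensitivity analyses and the change categories. This is a minor correction, worth making because the case is prespecified and the remedy is trivial.

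**What to change.** In SAP 5.5.2, replace the zero-baseline expression by treatment-period frequency × 100, and state that this is the ordinary formula with 1 added to both periods for these patients. A patient with no seizures in either period then scores 0%, and every randomized and dosed patient with treatment-period data keeps a value in the ITT percentage-change analyses. Do not set the value to missing: the SAP excludes zero-baseline patients for other seizures and individual seizure types, but doing so here would drop randomized, dosed patients from analyses on the ITT set.

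The cost is one formula, the matching line of derivation code, and an entry in the SAP amendment log (section 7) if made before unblinding. If made afterwards, it belongs in the clinical study report as a deviation from the SAP, as Protocol section 13 provides. If no such patient was randomized, no output changes.
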